8.6.1 Requirements for Immediate Reporting of Serious Adverse Events

The minimum reporting requirements for immediate reporting of SAEs include:

1. Identifiable subject
2. Suspected drug product
3. Event description
4. Identifiable reporting

source In addition, the investigator

must:

1. Report all SAEs to the relevant IRB/IEC within the timeframe specified by the IRB/IEC.
2. Submit follow-up reports to the sponsor Global Clinical Safety and Pharmacovigilance/designee and the Medical Monitor until the SAE has resolved, or, in the case of permanent impairment, until stabilized.
3. Ensure that the AE term(s) and causality assessment for all SAEs is entered in the eCRF.

If the minimum requirements for reporting are fulfilled, the investigator should not wait to receive additional information to fully document the event before notifying the sponsor/designee.

When submitting SAE reports to the sponsor/designee, subjects should be identified only by their subject number and study number. The investigator should not include the subject's name and address.

SAE update reports can be submitted to the sponsor/designee any time that additional relevant information becomes available. In cases of death, the investigator should supply the sponsor/designee and the IEC/IRB (as applicable, see [Section 8.7](#)) with any additional requested information as it becomes available (eg, autopsy reports and detailed medical reports). Once an SAE is reported to the sponsor/designee's Safety Group, a Safety Specialist may contact the investigator with follow-up questions.

The procedure to be followed if an ongoing AE becomes an SAE after the end of the observation period for AEs is described in [Section 8.9](#).

8.7 REPORTING OF SERIOUS ADVERSE EVENTS BY INVESTIGATOR TO IEC/IRB

The timeframe within an IEC/IRB must be notified of a death or an unexpected SAE considered at least possibly related to the IMP is stipulated by each individual IEC/IRB. The investigator is responsible for complying with the requirements for IEC/IRB notification. The investigator will notify the relevant IEC/IRB within the applicable timeframe by forwarding the

ZX008 (Fenfluramine Hydrochloride)
ZX008-1601 Clinical Study PA 4.0 (Japan) 25 July 2022

safety report (eg, MedWatch/CIOMS form) completed by the sponsor/designee for the notifiable event.

8.8 REPORTING OF EVENTS OTHER THAN SERIOUS ADVERSE EVENTS BY INVESTIGATOR TO SPONSOR

Even if none of the criteria for an SAE are fulfilled, any of the following events must be reported by the investigator to the Medical Monitor within 72 hours from the time the investigator is notified.

1. Hypersensitivity reactions
2. Pulmonary hypertension
3. Cardiac symptoms requiring intervention, or valvulopathy, if identified outside of study-related monitoring

8.9 FOLLOW-UP OF ADVERSE EVENTS

Every effort should be made to follow-up subjects who continue to experience an AE or an SAE on completion of the study or until the AE resolves. All follow-up information (and attempted follow-up contacts) should be documented in the subject's medical records. Details of the subject's progress should also be submitted to the sponsor/designee's Global Clinical Safety and Pharmacovigilance and the Medical Monitor.

Subjects who are discontinued from the study or complete the study and have been found to have any signs of valvulopathy or pulmonary hypertension on ECHO will be followed until the condition has resolved or stabilized where no further changes are likely, for a minimum of 6 months from the last dose of study medication, unless it is determined after unblinding that the subject did not receive ZX008.

8.9.1 Follow-up of Echocardiogram Findings

All ECHOs will be evaluated by a central reader, in consultation with the ICAB, if warranted. Findings related to pulmonary hypertension or valvulopathy on any of the four valves (aortic, mitral, pulmonary, tricuspid) will be reported to the investigator with grades of normal, trace, mild, moderate or severe. If the ECHO result has progressed in severity since the last reading then new oversight measures will be enacted as described below in Table 18 which describes the severity of ECHO findings with the level of increasing oversight if the subject is to remain in the study.

Table 18: Clinical Measures Enacted Upon Increasing Severity of ECHO Findings

| Severity | Valve | | | |
|-------------------|---------|---------|-----------|-----------|
| | Aortic | Mitral | Pulmonary | Tricuspid |
| Trace (<18 years) | Level 2 | Level 2 | Level 1 | Level 1 |
| Trace (>18 years) | Level 1 | Level 1 | Level 1 | Level 1 |
| Mild (<18 years) | Level 2 | Level 2 | Level 1 | Level 1 |
| Mild (>18 years) | Level 2 | Level 1 | Level 1 | Level 1 |
| Moderate | Level 3 | Level 3 | Level 3 | Level 3 |
| Severe | Level 3 | Level 3 | Level 3 | Level 3 |

Level 1: Continue per protocol

ZX008 (Fenfluramine Hydrochloride)
ZX008-1601 Clinical Study PA 4.0 (Japan) 25 July 2022

Level 2:

1. If there is a desire to continue study medication:
 - a. The investigator will evaluate the efficacy to date based on study diaries and consult with the parent/guardian, and determine whether study treatment was associated with significant, meaningful benefit in number, severity and/or duration of seizures and/or on the impact on daily functioning.
 - b. The investigator will consider whether the subject has had reasonable trials (dose and duration) of other available anticonvulsants (eg, valproic acid, clobazam, or topiramate), alone or in combination, and not maintained the level of seizure control achieved with study medication.
2. If the investigator feels consideration of continued treatment is warranted considering benefit and potential risk, and the parent/guardian feels strongly that the subject be maintained on the study medication when understanding the risks, the parent/guardian must sign a new consent which describes the additional risks and the subject should provide assent if appropriate.
 - a. If both of these conditions are not met, the subject is discontinued from treatment.
3. The investigator prepares a case history and rationale for continuation to be submitted to the IDSMC for review, including consideration of effects on seizures and comorbidities.
4. The cardiac reviewers (from the central reader, and potentially ICAB) prepare an evaluation of the cardiopulmonary risks and proposed monitoring plan if applicable, for submission to the IDSMC.
5. IDMSC will review the submissions from the Investigator and cardiac central reader and unblind the subject treatment if warranted.
6. IDSMC makes a determination of appropriate path, including the possible outcomes:
 - a. Discontinue study medication
 - b. Increase frequency of ECHO and ECG monitoring
 - c. Add additional ECG and/or ECHO measures to be monitored
 - d. Reduce the dose of study medication

Level 3:

1. The investigator will evaluate efficacy to date based on study diaries and consult with the parent/guardian, and determine whether the achieved benefit justifies the consideration of continuing study treatment by the IDSMC. MINIMAL efficacy criteria for IDSMC consideration:
 - a. Seizures must be more than 75% improved (number of motor seizures per 28 days) on treatment over baseline, and improvement must be consistent.
 - b. The number, type, duration, and distribution of seizures at baseline should be of a severity, which justifies the risks of cardiopulmonary complications, considering the subject's age and overall health.
 - c. Subject has had reasonable trials (dose and duration) of other available anticonvulsants (eg, valproic acid, clobazam, topiramate), alone or in

ZX008 (Fenfluramine Hydrochloride)
ZX008-1601 Clinical Study PA 4.0 (Japan) 25 July 2022

combination, and not maintained the level of seizure control achieved with study medication.

2. If the investigator feels consideration of continued treatment is warranted considering benefit and potential risks, and the parent/guardian feels strongly that the child be maintained on the study medication when understanding the risks, the parent/guardian must sign a new consent, which describes the additional risks and the child should provide assent if possible.
 - a. If both of these conditions are not met, the subject is discontinued from treatment.
3. The investigator prepares a case history and rationale for continuation to be submitted to the IDSMC for review, which includes effects of study medication on seizures and comorbidities related to LGS.
4. The cardiac reviewers (from the central reader, and potentially ICAB) prepare an evaluation of the cardiopulmonary risks and proposed monitoring plan if applicable, for submission to the IDSMC.
5. IDSMC will review the submissions from the Investigator and cardiac central reader and unblind the subject treatment if warranted.
6. IDSMC makes a determination of appropriate path, including these possible outcomes:
 - a. Discontinue study medication
 - b. Increase frequency of ECHO and ECG monitoring
 - c. Add additional ECG and/or ECHO measures to be monitored

8.10 PREGNANCY

This study is open to female and male subjects. Whenever possible, a pregnancy in a female subjects or the female partner of a male subject exposed to IMP should be followed to term so as to assess any potential occurrence of congenital anomalies or birth defects. Any follow-up information, including premature termination and the status of the mother and child after delivery, should be reported by the investigator to the sponsor/designee using a pregnancy reporting/outcome form.

9. DATA HANDLING PROCEDURES

9.1 RECORDING OF DATA

The investigator (or delegate) will maintain individual records for each subject. These records should include dates when a subject visited the study site, study-required information and data, and other notes as appropriate. These records constitute source data.

An eCRF and a subject diary will be provided by the sponsor (or delegate) for each subject enrolled into the study. Study site staff will enter data directly into the validated electronic data capture (EDC) system by completing the eCRF via a secure internet connection. The investigator is responsible for ensuring accurate and proper completion of the eCRF and subject diary for recording data according to the instructions given in the eCRF and subject diary.

All entries in the eCRF must be backed up by the relevant source data at the study site. All source data will be kept according to all applicable regulatory requirements (see [Section 12.8](#)). Source data must follow good documentation practices, be completed legibly for each subject

ZX008 (Fenfluramine Hydrochloride)
ZX008-1601 Clinical Study PA 4.0 (Japan) 25 July 2022

enrolled into the study and signed by the investigator (or delegate).

Data entry in the eCRF and subject diary must be completed in a timely manner so that they always reflect the latest observations on the subjects enrolled in the study.

The subject's diary will be completed by the parent/caregiver at home. Data entries will be reviewed by the investigator for completion and consistency.

9.2 DATA QUALITY ASSURANCE

An initiation meeting will be held before starting the study, during which the study design, procedures to be followed, and measures for ensuring standardized performance will be explained by a delegate from the sponsor, and a common understanding of the requirements of the study will be reached with the investigator and other relevant personnel at the study site.

Data generated throughout the study will be monitored and the data entered in the eCRFs will be checked against the subject records for completeness and accuracy. The sponsor's study monitor will perform this function.

The computer system used for study data handling will be fully FDA 21 CFR Part 11 compliant. All creation, modification or deletion of electronic study records will be documented through an automated Audit Trail. Following completion of eCRF pages and entry of the data into a database, the data will be checked electronically for consistency and plausibility. Data queries will be generated for questionable data and response clarification will be sought from the investigator. These data queries must be resolved in a timely manner by the investigator (or delegate).

9.3 RECORD RETENTION

A study document binder will be provided by the sponsor for the investigator at each site for all requisite study documents (constituting the "Investigator Study File").

Following completion of the study, the investigator will retain copies of the approved study protocol, ICF, relevant source documents, and all other supporting documentation related to the study according to applicable regulatory requirements.

The investigator is responsible for archiving the Investigator Study File, the subject's records, and the source data according to applicable regulatory requirements. These documents have to be archived for at least 15 years or at least 2 years after the last approval of a marketing application in an ICH region, but should be retained for longer if required by regulatory requirements or by agreement with the sponsor.

If the investigator can no longer maintain the archive of study records (eg, due to retirement or relocation), the sponsor must be informed in writing about any change in responsibility for record retention, including the name of the new responsible party, contact information, and location of the study records. Records may not be destroyed without prior written consent from the sponsor.

ZX008 (Fenfluramine Hydrochloride)
ZX008-1601 Clinical Study PA 4.0 (Japan) 25 July 2022

10. STATISTICS

10.1 STATISTICAL ANALYSIS: PART 1

The primary analyses of the study will be performed on data from Part 1 Cohort A after the last subject enrolled in Cohort A has completed the last study visit of Part 1. Data from Part 1, Cohort B will be analyzed independently after the last subject in Cohort B completes Part 1. An interim analysis of Part 2 will be performed after all Cohort B subjects complete 12 months in Part 2. A secondary analysis will be conducted after the last Cohort B subject has enrolled and completed the last study visit of Part 2. Analysis results for Part 1 from Cohort A and Cohort B will be compared through descriptive statistics, and if reasonable, some analysis may be performed using data from Cohort A and Cohort B combined. Subjects randomized to 0.5 mg/kg/day (ie, those taking concomitant STP) will be grouped with subjects randomized to 0.8 mg/kg/day for all efficacy analyses.

10.1.1 DETERMINATION OF SAMPLE SIZE

The sample size for Part 1 Cohort A was estimated under the assumption that adding ZX008 at 0.8 mg/kg/day to current therapy will lead to a mean decrease in drop seizures that is 30 percentage points greater than adding placebo to current therapy. For example, if adding placebo leads to a 10% decrease in seizures, then adding the high dose of ZX008 would be expected to decrease seizures by at least 40%.

The variability expected in the trial was estimated from a Phase 3 trial of clobazam for patients with Lennox-Gastaut syndrome (Ng 2011) leading to an assumption that the SD is 50%. Other assumptions include an allowance for 20% dropouts between randomization and the start of the maintenance period.

Under these assumptions, and using a Wilcoxon rank-sum test to approximate the primary comparison between the ZX008 0.8 mg/kg/day and placebo groups, a sample size of 63 subjects per treatment group affords 90% power to detect a difference between groups that is significant at the $\alpha=0.05$ level. Assuming a 20% drop-out rate prior to the start of the maintenance period yields a requirement for an additional 16 subjects per group for a total of 79 subjects per treatment group. Similar calculations for the 0.2 mg/kg/day ZX008 group lead to a total required sample size of 237. The number of subjects randomized into Part 1 Cohort A is estimated to be approximately 250 due to the long baseline period.

The sample size of 10 to 15 subjects per treatment group in Cohort B is expected to provide a descriptive assessment of whether the treatment effect in Japanese subjects is similar that observed in Cohort A subjects from the rest of the world.

10.1.2 ANALYSIS POPULATIONS

10.1.2.1 Safety (SAF) Population

All Part 1 safety analyses will be performed on the SAF Population defined as all randomized subjects who receive at least one dose of ZX008 or placebo.

ZX008 (Fenfluramine Hydrochloride)
ZX008-1601 Clinical Study PA 4.0 (Japan) 25 July 2022

10.1.2.2 Modified Intent-to-Treat (mITT) Population

The mITT Population is defined as all randomized subjects who receive at least one dose of ZX008 or placebo and for whom at least one week of diary data are available. Subjects will be analyzed according to the treatment group to which they were randomized. The primary comparison of ZX008 0.8 mg/kg/day to placebo, who complete at least 4 weeks of diary data in the maintenance period, as well as key secondary analyses, will be performed on the mITT Population.

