In an integrated analysis of safety of the double-blind studies, 117 (95.9%) subjects in any ZX008 treatment group and 68 (81.0%) subjects in the combined placebo group reported at least 1 TEAE. The most common ($\geq 10\%$) TEAEs reported in subjects receiving any dose of ZX008 were: blood glucose decreased, constipation, decreased appetite, diarrhea, echocardiogram abnormal, fall, fatigue, lethargy, nasopharyngitis, pyrexia, seizure, somnolence, status epilepticus, tremor, upper respiratory tract infection, vomiting, and weight decreased. All of the echocardiogram abnormal TEAEs were trace mitral or trace aortic valve regurgitation, which are normal physiological findings seen in healthy children ([Webb 2015](#)). A total of 15 (12.3%) subjects in any ZX008 treatment group and 11 (13.1%) subjects in the combined placebo group reported at least 1 serious TEAE. The most frequently reported ($\geq 5\%$) serious AEs (SAEs) were status epilepticus and seizure. A total of 76 (62.3%) subjects in any ZX008 treatment group and 22 (26.2%) subjects in the combined placebo group reported a TEAE determined by the Investigators to be related to the study drug, and 3 (2.5%) subjects in any ZX008 treatment group and 1 (1.2%) subject in the combined placebo group reported a serious TEAE determined to be related to the study drug. During the double-blind treatment periods, 7 (5.7%) subjects in any ZX008 treatment group and 1 (1.2%) subject in the combined placebo group reported a TEAE that lead to discontinuation from study participation. There were no deaths during the double-blind treatment periods.

Subjects in Study 1 and Study 1504 if eligible could participate in Study 1503, an open-label long-term, safety extension study that is currently ongoing. All subjects in Study 1503 started ZX008 at 0.2 mg/kg/day and could flexibly titrate to a maximum dose of 0.8 mg/kg/day, maximum 30 mg/day (if not receiving a concomitant STP regimen) or 0.5 mg/kg/day, maximum 20 mg/day (if receiving concomitant STP regimen), based on effectiveness, safety and tolerability. Though primarily a safety study, subjects in Study 1503 maintained a daily seizure diary and continued to complete rating scales on overall effectiveness and quality of life measures.

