10.1.5 TREATMENT PERIODS

Baseline Period

The Baseline Period covers the 28 days immediately prior to randomization. The baseline frequency of seizures that lead to drops will be calculated from data collected during this period.

Titration Period

The Titration Period covers the first 14 days of treatment while subjects are titrated to their randomized dose. It begins on the first full day of treatment (Study Day 1) and extends through Study Day 15 regardless of the exact day on which a subject reaches his or her assigned dose. The Titration Period applies to all subjects including placebo recipients.

Maintenance Period

The Maintenance Period covers the 12 weeks following the end of the titration period. It begins on Study Day 16 and extends through Study Day 99.

Titration +Maintenance (T+M) Period

The T+M period combines the Titration and Maintenance periods, beginning on Study Day 1 and extending through Study Day 99. The T+M period is considered the treatment period.

Taper/Transition Period

The Taper/Transition Period begins immediately at the end of T+M period and extends to Visit

ZX008 (Fenfluramine Hydrochloride)
ZX008-1601 Clinical Study PA 4.0 (Japan) 25 July 2022

13, 2 weeks later; ie, from Study Day 99 through Study Day 113.

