10.1.6.1 Efficacy Analyses

Primary Efficacy Analysis

The primary efficacy endpoint for Part 1 is the percent change in frequency of seizures that result in drops (DSF: drop seizure frequency) per 28 days between the combined Titration and Maintenance (T+M) and Baseline periods in Cohort A. The DSF will be calculated from all available data collected during the Baseline and T+M Periods without imputation. The percent change from baseline DSF will be calculated as the the change in DSF between T+M and Baseline / DSF during Baseline \times 100. Both the mean and median percent change in DSF Both the mean and median percent change in DSF will be presented.

The primary endpoint will be assessed using a nonparametric, rank analysis of covariance (ANCOVA) with treatment group (ZX008 0.8 mg/kg/day, ZX008 0.2 mg/kg/day or placebo) and weight group (<37.5 kg, \geq 37.5 kg) as factors; rank baseline DSF as a covariate; and rank percent change in DSF from baseline as the response variable. The primary analysis will compare the ZX008 0.8 mg/kg/day group to the placebo group at the $\alpha=0.05$ level of significance. The difference between the ZX008 0.8 mg/kg/day group and the placebo group in percent change in DSF, and its 95% confidence interval, will be estimated using the Hodges-Lehmann method.

As a sensitivity analysis, the primary endpoint will also be analyzed using a parametric ANCOVA that incorporates treatment group and weight group as factors; log baseline DSF as a covariate; and log DSF during T+M as the response variable. Significance will be assessed by a model contrast that compares the ZX008 0.8 mg/kg/day group to the placebo group. The size of the treatment effect will be estimated by exponentiating the difference between the ZX008 0.8 mg/kg/day group and the placebo group derived from the model. Another sensitivity analysis will compare the ZX008 0.8 mg/kg/day group to the placebo group using a Wilcoxon rank-sum test.

Key Secondary Analyses

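### Protocol Section 10.1.2.2 gives two incompatible rules for the primary analysis set: one week of diary data, or four weeks of Maintenance diary data

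*Protocol*

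**What the plan says.** Section 10.1.2.2 defines the mITT Population in these terms: "all randomized subjects who receive at least one dose of ZX008 or placebo and for whom at least one week of diary data are available", analysed by randomized group. Its last sentence names the primary comparison and attaches a further condition to it: "The primary comparison of ZX008 0.8 mg/kg/day to placebo, who complete at least 4 weeks of diary data in the maintenance period". The same sentence ends "as well as key secondary analyses, will be performed on the mITT Population".

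Section 10.1.5 says of the Maintenance Period: "It begins on Study Day 16 and extends through Study Day 99". The primary endpoint covers a longer window, Titration plus Maintenance (T+M) from Study Day 1: "The T+M period is considered the treatment period". Section 10.1.6.1 adds "The DSF will be calculated from all available data collected during the Baseline and T+M Periods without imputation".

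Section 10.1.1 sizes the trial at 63 evaluable subjects per group. It adds 16 per group for an assumed 20% loss before Maintenance, which gives 79 per group and 237 in all.

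**The concern.** The section names one population and describes two. A subject who stops on Day 20 with a complete diary is in the mITT Population as defined but fails the four-week condition. The main clause of the last sentence keeps that subject in the primary comparison, and the relative clause removes them.

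The choice matters because the four-week condition selects on something that happens after randomization. Staying through titration and the first four weeks of Maintenance depends on tolerability and seizure control, and treatment can affect both. A comparison restricted to stayers is no longer protected by randomization. It also discards subjects who have data for the primary endpoint, since that endpoint counts from Day 1.

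The clause is attached to the primary comparison only. Step 1 of the testing hierarchy (percent change in drop seizure frequency, DSF) could then use one set and step 2 (the 50% responder rate, derived from the same variable) another. Section 10.1.6.1 applies the same methods to Cohort B. With 10 to 15 subjects per group there, a 20% loss would be 2 to 3 subjects per group.

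**Working it through.** **Inputs.** Effect 30 percentage points, SD 50, alpha 0.05, power 90%, 63 per group, 20% loss before Maintenance, 79 per group, 237 total (Section 10.1.1). Maintenance is Days 16 to 99 (Section 10.1.5). Alpha is taken as two-sided: the one-sided normal-approximation figure is 48 per group, too low to lead to 63.

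**Reproducing the plan's sample size.**
- A two-sample t-test for 30 points with SD 50 needs 60 per group.
- Dividing by the Wilcoxon efficiency under normality, 3/π: 60 / 0.955 = 62.8, so 63. Simulated Wilcoxon power at 63 per group is 90.5%.
- Loss allowance: 63 / 0.80 = 78.75, so 79, which is 16 more per group. Total 3 × 79 = 237.

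The stated figures reproduce, so the sample-size arithmetic is not at fault.

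**What each rule requires.**
- mITT definition: 7 diary days. The period is not stated. Section 6.1.1.3 already requires at least 28 days of prospective diary at the randomization visit, so read literally the rule excludes no one who was dosed.
- Four-week clause: 28 Maintenance diary days. The earliest completion is Day 16 + 27 = Day 43.

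**Who is lost if the clause is applied.** Everyone who leaves before Maintenance fails it. On the plan's own allowance that is 16 of 79 per group, or 48 of 237. Departures between Day 16 and about Day 43 add to this. Subjects who leave after at least a week on treatment can have enough T+M diary data to meet the one-week rule.

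**Power under each reading** (normal approximation with effective n = n × 3/π; power = Φ(effect / (SD × √(2 / effective n)) − 1.96)).

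| Reading | Assumption | n per group | Power |
|---|---|---|---|
| Four-week | 20% lost by Day 43 | 63 | about 91% |
| Four-week | 25% lost (assumed) | 59 | about 89% |
| Four-week | 30% lost (assumed) | 55 | about 87% |
| One-week | 16 early active leavers with no effect | 79 | about 83% |
| One-week | the same 16 with half the effect | 79 | about 91% |
| One-week | the same 16 with the full effect | 79 | about 96% |

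In the no-effect row the mean effect is 30 × 63/79 = 23.9 points.

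**Illustration of the estimate.** If a fraction f of the active arm leaves early with no benefit and is excluded, an effect of 30 among stayers corresponds to 30 × (1 − f) among all treated. The only active-arm discontinuation rate in the document that bears on this is in Section 1.3: "7 (5.7%) subjects in any ZX008 treatment group and 1 (1.2%) subject in the combined placebo group reported a TEAE that lead to discontinuation". With f = 0.057, 30 × 0.943 = 28.3 points, and 30 / 28.3 = 1.06, an overstatement of about 6%. This supposes that every such exit came before Day 43 with no benefit. It is arithmetic on means, whereas the planned estimate is a Hodges-Lehmann difference, so it indicates scale only.

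**The case against.** The sentence is ungrammatical, and its main clause says that the primary comparison is performed on the mITT Population. The four-week wording appears nowhere else: neither the synopsis nor the primary analysis text in Section 10.1.6.1 contains it. It may be leftover text. This stands. A reader might infer that the plan definitely excludes early dropouts, but the document does not settle that. The defect is two unreconciled rules.

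A reader might also infer a conflict with the all-available-data rule in Section 10.1.6.1. That rule says how each subject's DSF is calculated and can be followed in any subset. It makes the inclusive reading more natural but does not say who is analysed. Section 10.1.1, which sets aside subjects lost before Maintenance, fits the restrictive reading equally well.

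The most tempting inference is that the exclusions would favour the drug. The figures in Section 1.3 do not show this. They come from Dravet syndrome studies, pool three doses, count only discontinuations for adverse events, and cover the whole double-blind period. Section 4.5 provides for withdrawal for clinically significant seizure worsening, which could fall on placebo and push the other way. Taking the 20% allowance as an active-arm rate with no benefit would give 24 points and a 25% overstatement. But that allowance applies to every arm for sample-size purposes, and no observed rate supports it.

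Finally, Section 10.1.6 leaves full methods to the SAP. That does not remove the point, because the protocol states two incompatible rules, which is different from leaving a detail open.

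**Conclusion.** The point holds as an internal contradiction that leaves the primary analysis set undetermined. The minimum follow-up is either one week of diary data or diary data to at least Day 43. On the protocol's own allowance, the stricter rule would remove at least 16 of 79 subjects per group from the primary comparison, would condition it on retention after randomization, and could separate it from the key secondary analyses.

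The count of 16 rests on the 20% planning assumption; actual losses are not in the document. The direction and size of any bias cannot be established from the protocol. The 28.3-point figure is an illustration under a no-benefit assumption and a rate from another syndrome.

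**What to change.** In Section 10.1.2.2:
- Delete the four-week clause.
- State that the primary and key secondary analyses use all mITT subjects as randomized.
- Specify that the one week of diary data is post-baseline T+M data. Every randomized subject should already have 28 days of baseline diary, so without this the requirement does nothing.
- Keep the subset with at least four weeks of Maintenance diary only as a labelled sensitivity analysis.

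Align the dropout reasoning in Section 10.1.1 with the chosen set, since it now treats subjects lost before Maintenance as not evaluable. Section 3.6 describes randomization running to June 2019, well before this amendment. The correction should therefore record which rule was fixed before unblinding, so that the set is traceable and not chosen between two readings once data exist.

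The cost is one sentence, plus a matching line in the SAP if it repeats the clause, and one extra sensitivity table. Power could fall below 90% if early leavers gain little (about 83% if they gain nothing). The one-week rule still drops a few randomized subjects, but far fewer than the four-week rule.
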